## 2.6 Checkpoint Blockade in Myeloma

PD-1 expression is upregulated on T-cells isolated from patients with MM, suggesting that this pathway is of importance in mediating the immunosuppressive state in this patient population. However, PD-1 blockade has demonstrated minimal single agent activity in MM due to the lack of the intrinsic anti-tumor immunity in this setting. Efforts are underway to assess the activity of combination therapy with immunomodulatory agents and PD-1 antibody. Phase II studies demonstrated that PD-1 blockade in conjunction with IMID therapy resulted in clinical activity in a subset of patients with advanced disease who were refractory to single agent therapy with IMIDs. However, a randomized trial demonstrated increased morbidity and mortality was noted in patients treated with combination IMID therapy and PD-1 blockade. We postulate that the DC/MM fusion vaccine will act synergistically with checkpoint blockade by inducing the expansion of myeloma specific T cells that can be further activated by exposure to checkpoint blockade. Indeed, preclinical studies from our laboratory demonstrated that PD-1 blockade enhances T-cell response to DC/MM fusions in vitro.

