### 2.5.5 Toxicology

A maximum tolerated dose (MTD) of nivolumab was not defined. Serious adverse events (SAEs) occurred in 32 of 296 patients (11%) similar to the immune-related inflammatory events seen with ipilimumab: pneumonitis, vitiligo, colitis, hepatitis, hypophysitis, and thyroiditis (with noted pulmonary toxicity resulting in 3 deaths. Renal failure, symptomatic pancreatic and DM, neurologic events, and vasculitis have also been reported.).

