### **7. IDENTIFICATION OF TREATMENT LIMITING TOXICITIES**

Treatment limiting toxicities (TLT) will be defined as toxicity judged to be possibly or definitely related to the study treatment and meeting the following criteria:

- Grade 3 or higher non-hematologic toxicities that do not resolve within 14 days of onset;
  - Please note the following exceptions that necessitate immediate discontinuation of therapy:
    - Grade 4 creatinine elevation
    - Grade 3 or higher pulmonary toxicity
    - Grade 3 or higher ALT, AST or total bilirubin elevation
    - Grade 3 or higher adrenal insufficiency
    - Grade 3 or higher neurological adverse event
    - Grade 3 or higher myocarditis
- Grade 4 or higher clinically significant non-hematologic toxicities;
- Grade 4 or higher hematologic toxicities that do not resolve to grade 1 or baseline within 7 days of onset;
  - Please note that this excludes lymphopenia, as mentioned in section 5.9.3;
- Grade 4 or higher nivolumab infusion reactions.

Patients experiencing TLT will not receive further therapy

If 3 or more patients experience a TLT within the first 28 days of initiating therapy among the first 10 patients enrolled, then accrual will be suspended. TLTs will be defined per the above criteria with grades determined by CTCAE version 4.0 that are possibly, probably or definitely related to the study treatment. Patients will be monitored for the occurrence of TLTs during the first 28 days of treatment.

Once the 10th participant is enrolled, accrual will be paused until the 10th participant completes a full cycle of treatment (28 days) without experiencing any TLTs.

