#### 13.2 Data Safety Monitoring

The DF/HCC Data and Safety Monitoring Committee (DSMC) will review and monitor toxicity and accrual data from this study. The committee is composed of medical oncologists, research nurses, pharmacists and biostatisticians with direct experience in cancer clinical research. Information that raises any questions about participant safety will be addressed with the Overall PI and study team.

The DSMC will review each protocol up to four times a year with the frequency determined by the outcome of previous reviews. Information to be provided to the committee may include: up-to-date participant accrual; current dose level information; TLT information; all grade 2 or higher unexpected adverse events that have been reported; summary of all deaths occurring within 30 days of intervention for Phase I or II protocols; for gene therapy protocols, summary of all deaths while being treated and during active follow-up; any response information; audit results, and a summary provided by the study team. Other information (e.g. scans, laboratory values) will be provided upon request.

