As a secondary clinical endpoint, response will be assessed according to IMWG response criteria. In a prior phase I trial of DC/MM vaccination in patients with relapsed MM, 69% (11/16) patients had disease stabilization. No patients demonstrated disease response (PR, VGPR, or CR). In the present phase II trial, overall response rate per IMWG criteria will be assessed. An exact binomial test with a 10% one-sided significance level will have 82% power to detect the difference between the ORR proportion of 0.15 (null hypothesis) and the alternative ORR proportion of 0.35 when the sample size is 25. An ORR of 35% is considered worthy of further study in a larger trial.

If 3 or more patients experience a TLT, accrual will be suspended.

	True but Unknown Rate of DLT				
	0.10	0.20	0.25	0.30	0.40
Probability of continuation of enrollment ( $\leq 2$ TLT in 10 pts)	0.930	0.678	0.526	0.383	0.167

If the true rate of TLT is 25%, the probability of observing 2 or fewer TLTs within a cohort of 10 patients is 0.526.

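### Sections 7 and 14.1 count a treatment-related death as one TLT of three, so two related deaths among the first 10 patients, with no other TLT, do not trigger suspension of accrual

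*Combined protocol and SAP*

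**What the plan says.** **The rule.** Section 7 suspends accrual "If 3 or more patients experience a TLT within the first 28 days of initiating therapy among the first 10 patients enrolled". Section 14.1 restates it with no window or cohort in the sentence: "If 3 or more patients experience a TLT, accrual will be suspended". The table beneath that sentence is for 10 patients.

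**How a death enters.** Section 7 has no criterion for death. A related grade 5 event is a TLT through open-ended items such as "Grade 4 or higher clinically significant non-hematologic toxicities", and it adds one to the count. A related non-hematologic grade 3 event still unresolved on day 15 also adds one.

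**Attribution.** The definition opens with "toxicity judged to be possibly or definitely related to the study treatment". A later sentence in the same section also includes probable relation.

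**The scheduled pause.** Accrual stops once the tenth participant is enrolled, until that "participant completes a full cycle of treatment (28 days) without experiencing any TLTs".

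**What else happens after a death.** Section 8.3.1 requires immediate notice of life-threatening complications to the Overall PI. Section 8.3.3 sets a 24-hour or one-business-day reporting time for grade 5 events. Section 8.4 covers expedited FDA reports. Section 13.2 lists, among material that may go to the DSMC, a "summary of all deaths occurring within 30 days of intervention for Phase I or II protocols". That committee reviews the protocol up to four times a year, and safety questions are taken up with the Overall PI and study team. None of these sections attaches suspension of accrual to a death.

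**Background.** Section 2.5.5 describes serious adverse events in 32 of 296 patients on nivolumab, "with noted pulmonary toxicity resulting in 3 deaths". Section 2.6 reports that "a randomized trial demonstrated increased morbidity and mortality was noted in patients treated with combination IMID therapy and PD-1 blockade".

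**The concern.** The three-TLT rule is the only numeric safety boundary in the plan. It weighs a related death no more heavily than a prolonged grade 3 event. For an individual patient, section 7 does separate out severe pulmonary, hepatic, adrenal, neurological and cardiac events as exceptions that need immediate discontinuation. The trial-level count makes no such distinction, even for death.

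The combination is also new. Section 2.6 supports vaccine plus PD-1 blockade with in vitro work and a postulated synergy, and section 2.7 lists toxicity among the things the trial will examine. Followed as written, the plan would keep enrolling after two related deaths unless someone used discretion to stop. That discretion would fall largely to the Overall PI, who under section 8.4 is also the sponsor.

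**Working it through.** **Inputs.** From section 7: threshold 3, cohort 10, window 28 days. From section 14.1: the continuation table and 25 planned patients. From section 2.5.5: 3 deaths and 296 patients. The related-death rate d for this combination is not in the documents, so it is assumed over 1% to 20%. Patients are treated as independent, and all 10 (or 25) are taken to start treatment.

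**Step 1: reproduce the plan's table.** P(continue) = (1−p)^10 + 10p(1−p)^9 + 45p²(1−p)^8. At p = 0.25 this is 0.0563 + 0.1877 + 0.2816 = 0.5256. At 0.10, 0.20, 0.30 and 0.40 it gives 0.9298, 0.6778, 0.3828 and 0.1673. All five stated values (0.930, 0.678, 0.526, 0.383, 0.167) agree.

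**Step 2: two deaths against the threshold.** Two related deaths and no other TLT give a count of 2. Since 2 < 3, suspension is not triggered.

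**Step 3: the scheduled pause.** It begins at the tenth enrolment whatever has happened before. It ends on the tenth participant's own 28 days. Deaths in patients 1 to 9 neither start it earlier nor prolong it.

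**Step 4: a background rate.** 3/296 = 1.0%, if 296 is the denominator for those deaths. The text gives it for serious adverse events and does not limit the deaths to 28 days.

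**Step 5: continuation after 10 patients if deaths are the only TLTs.** The current rule uses the Step 1 formula with p = d. A trigger at the first related death gives (1−d)^10. The last column is P(2 or more deaths) = 1 − (1−d)^10 − 10d(1−d)^9.

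| Assumed d | Current rule | First-death trigger | P(2 or more deaths in 10) |
|---|---|---|---|
| 1% | 0.9999 | 0.904 | 0.004 |
| 2% | 0.9991 | 0.817 | 0.016 |
| 5% | 0.9885 | 0.599 | 0.086 |
| 10% | 0.930 | 0.349 | 0.264 |
| 20% | 0.678 | 0.107 | 0.624 |

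**Step 6: deaths mixed with other TLTs.** With total TLT rate T, including deaths at rate d, the current rule plus a first-death trigger continues with probability (1−T)^10 + 10(T−d)(1−T)^9 + 45(T−d)²(1−T)^8. At T = 0.25 and d = 0.02 this is 0.0563 + 0.1727 + 0.2383 = 0.467, against 0.526 now.

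| Total TLT rate T | Current rule | Trigger added, d = 2% | Trigger added, d = 5% |
|---|---|---|---|
| 10% | 0.930 | 0.783 | 0.591 |
| 25% | 0.526 | 0.467 | 0.387 |

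**Step 7: cost of a first-death trigger.** P(at least one pause) = 1 − (1−d)^n.

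| True d | n = 10 | n = 25 |
|---|---|---|
| 1% | 1 − 0.904 = 9.6% | 1 − 0.778 = 22% |
| 2% | 1 − 0.817 = 18.3% | 1 − 0.603 = 40% |

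**The case against.** The other side has several sound points, and they limit what can be claimed.

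- **Excess mortality.** A reader might infer from section 2.6 that excess mortality is an established risk of this regimen in myeloma. The documents do not support that. The finding is for an IMiD with PD-1 blockade. No IMiD is part of study treatment, and section 5.4 prohibits IMiDs in bridging. The deaths in section 2.5.5 carry the same reference as the phase 1 study in section 2.5.4, where the responding tumours named are lung, melanoma and renal. No section reports deaths in myeloma from PD-1 blockade without an IMiD.
- **No pause at all.** A reader might infer that accrual would run on with no break. It would not, because accrual stops after the tenth enrolment. But that pause does not respond to earlier deaths, and it does nothing while the remaining places up to the tenth are filled.
- **Unreviewed deaths.** A reader might infer that deaths would escape review. Sections 8.3.1, 8.3.3 and 8.4 require notice and reporting, and section 13.2 allows DSMC review. The contrast in Step 5 is suspension triggered against not triggered, not reviewed against unreviewed.
- **Size.** Rates of 10% or 20% are assumptions. Near 1%, two related deaths in 10 are very unlikely (0.4%). When other TLTs are common, the added trigger changes continuation less: 0.526 to 0.467 at 2% deaths. The rule also already counts severe pulmonary and cardiac events that may precede a death.
- **Choice.** A first-death trigger is one of several reasonable designs. A trigger at two deaths hardly changes the figures (0.526 to 0.524 at T = 25% and d = 2%).

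All of this stands. None of it supplies a passage that suspends accrual because of a death. The low chance of two deaths at about 1% also cuts the other way: if two did occur, they would be hard to reconcile with that background rate, and the written rule would still not respond.

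**Conclusion.** The point holds as a gap in the monitoring rule. It is not an arithmetic error, since the section 14.1 table is correct. Two related deaths among the first 10 patients, with no other TLT, leave the suspension rule unmet, and no other section requires suspension.

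The practical size depends on a death rate that the documents do not give. If deaths are the only TLTs, the current rule continues with probability above 0.99 at 1–2%, 0.9885 at 5%, 0.930 at 10% and 0.678 at 20%. A first-death trigger would give 0.904, 0.817, 0.599, 0.349 and 0.107 at 1%, 2%, 5%, 10% and 20%. The supporting background is the three nivolumab deaths in section 2.5.5, not the IMiD combination in section 2.6. This is a cheap improvement to trial-level monitoring. It does not bear on any patient's treatment.

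**What to change.** Add one sentence to sections 7 and 14.1: a grade 5 event judged possibly, probably or definitely related to study treatment pauses accrual until the DSMC has reviewed it, in addition to the three-TLT rule.

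State whether the clause covers the first 10 patients or all 25, and whether the 28-day window applies. At the same time, reconcile the windowed rule in section 7 with the unrestricted sentence in section 14.1, and the two attribution lists within section 7.

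Add operating characteristics that match the chosen scope. A row in the present 10-patient table describes a 10-patient clause only; a clause covering 25 needs its own row.

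**Cost.** One sentence, one table row and no added patients. If the true related-death rate is only 1–2%, the chance of at least one pause is 10–18% over 10 patients or 22–40% over 25. Each pause is for review and does not close the trial.

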## 2.7 Rationale

MM is associated with immune suppression, including defects in antigen presentation and effector cell function that are thought to play a role in disease progression. Although the outcomes for myeloma patients have improved greatly over the past decade, the majority of patients relapse even after autologous stem cell transplant and post-transplant maintenance therapy with lenalidomide. We have demonstrated that vaccination with DC-MM fusions induces the expansion of myeloma reactive T cells and is associated with the conversion of partial to complete responses following high dose chemotherapy with stem cell rescue. We are currently conducting a national randomized multicenter trial under the auspices of the CTN cooperative oncology group, to assess the clinical and immunologic impact of vaccination with lenalidomide maintenance as compared to maintenance alone in myeloma patients undergoing autologous stem cell transplantation.

In a phase 1 trial published in 2011, we previously studied the role of personalized DC/MM fusion vaccination in the setting of relapsed MM. In this patient experience, we did observe an encouraging immunologic signal. However, only a subset of these relapsed MM patients had stable disease post-vaccination and no patient demonstrated a reduction in disease burden. For this reason, we postulate that in the relapsed MM disease setting, the combination of vaccination along with a second immunologic agent may yield disease response in addition to immunologic activation against MM. In the present proposal, we hypothesize that the efficacy of checkpoint blockade in myeloma is dependent on the initial expansion of myeloma-reactive T cells in the immune repertoire that can then be further activated and expanded in the context of nivolumab therapy. We propose a clinical trial to examine the toxicity, immunologic effect and clinical response of nivolumab administered in conjunction with the DC/MM vaccine, as vaccination alone in this patient population has not previously yielded clinical disease response. We hypothesize that the study will illuminate the nature of the immunologic response to a therapeutic strategy that incorporates vaccine-mediated expansion of myeloma specific T cell immunity and antibody-mediated targeting of negative checkpoints that will alter the tumor microenvironment and favor the generation of a productive immune response targeting myeloma cells.

## 2.8 Correlative Studies Background

### 2.8.1 Impact of therapy on the immunologic response in the peripheral blood and bone marrow

The primary immunologic endpoint is to define the immunologic response to nivolumab and the DC/MM fusion vaccine with respect to the induction of peripheral blood myeloma-specific immunity in patients with relapse disease after prior proteasome inhibition, IMiD, and anti-CD38 mAb therapy. Specifically, we will compare the expansion of

treatment-induced myeloma-specific T cells in the circulation as measured by pre-therapy and peak post-treatment levels of CD4 and CD8 T cells expressing IFN $\gamma$  following ex-vivo exposure to autologous tumor lysate. Similarly, as a secondary endpoint and correlative study, we will quantify the percentage of myeloma-reactive lymphocytes in the bone marrow prior to cycles 1, 3, 6 and at the off-treatment time. The expansion of myeloma-specific T cells in the circulation and bone marrow will be calculated individually for each patient so that the specific baseline levels prior to vaccination will serve as an internal control value for each patient. To control for intrinsic variability of the assay, samples are cryopreserved and all time points are analyzed in a single experiment. To control for nonspecific reactivity against normal marrow elements, T cell expression of IFN $\gamma$  will be measured following pulsing with lysate from CD38- BMMCs (when feasible). We will determine the mean fold increase in myeloma-specific T cells and the percentage of patients demonstrating 3 and 10 fold threshold increases in response to vaccination in the circulation and the bone marrow.

We hypothesize that patients will demonstrate enhanced myeloma-specific immunity following exposure to vaccine plus nivolumab as compared to the pre-treatment time point. In a prior study, we observed that patients with multiple myeloma exposed to a MM/DC fusion vaccine had a mean log10-fold increase in myeloma-specific CD4+ T cells from pre-mobilization to post-transplant and from pre-mobilization to peak post-vaccination was 3.55 (95% CI 1.58;8.13) and 9.55 (95% CI 5.37;16.98), respectively. The mean log10 fold increase in myeloma-specific CD8+ T cells from pre-mobilization to post-transplant and from pre-mobilization to peak post-vaccination was 4.37 (95% CI 2.40;7.76) and 8.32 (95% CI 4.68;15.14), respectively. Similarly, in an early phase clinical trial of AML patients receiving AML/DC fusion vaccination following a chemotherapy-induced remission, we also observed enhanced leukemia-specific immunity as evidenced by increased circulating lymphocytes targeting leukemia cells.

### 2.8.2 Effect of treatment on circulating T cells binding the MUC1, NY-ESO, Survivin, PRAME, WT1 tetramers in HLA-A2.1 patients

We have previously observed enhanced antigen-specific reactivity in patients treated with personalized dendritic cell fusion vaccine therapy. We will examine antigen-specific reactivity by tetramer analysis in prior to and after exposure to the vaccine and nivolumab in HLA-A2.1 positive patients. This assay utilizes tetrameric proteins to detect and quantify T-cells that are specific for a given antigen within a peripheral blood sample. We hypothesize that patients treated with the combination of vaccine and nivolumab will elicit immune-specific responses against myeloma cells and thereby, we will observe increased T cells against common myeloma antigens including WT-1 and MUC-1. Functional characteristics of the pentamer positive cells will be determined by quantifying expression of IFN $\gamma$ , granzyme B, IL-4, and IL-10 expression by intracellular FACS staining.

### 2.8.3 Immune microenvironment including T cell subsets, T cell checkpoint receptors and myeloid-derived suppressor cells (MDSCs)

We plan on quantifying T cell subsets, T cell checkpoint receptors, and MDSCs via flow cytometry. Bone marrow aspirate and peripheral blood samples will be obtained prior to and after initiating immunotherapy and the microenvironment will be assessed with respect to the presence of Tregs, PD-1 expressing T cells, central memory (CD4/CD62L/CD27), effector memory (CD4/CD62L/CD27), and naïve T cells and granulocytic (CD11B+ CD33+ HLADRLOW/ CD15+) and monocytic (CD11B+ CD33+ HLADRLOW/ CD15-) MDSCs. We hypothesize that exposure to vaccine and PD-1 blockade with nivolumab will shift T cells from an immunoregulatory into an immune-activated phenotype and will also decrease MDSC burden in the microenvironment.

### 2.8.4 Optional Vaccine Site Biopsy

In patients who develop a vaccine site reaction, an optional biopsy of the vaccine site may be performed. Biopsy of the vaccine injection site will undergo immunohistochemical staining to assess for infiltrating lymphocytes which will be further characterized by mechanical disruption and flow cytometry to quantify recruitment of myeloma and antigen specific T cells. Presence of effector (CD62L/CD27) and central memory cells (CD62L/CD27) within the myeloma-specific and pentamer+ T cell populations will be determined by multichannel flow cytometry.

#### 2.8.5 Optional Aspirate and Peripheral Blood Samples for future research

In patients who consent to optional bone marrow aspirate and peripheral blood samples, we will cryopreserve these samples in the [name] laboratory for future possible use in biomarker discovery and correlative studies including genomic analysis, whole exome sequencing, RNA sequencing, neoantigen discovery, proteomics, microRNA profiling, as well as additional immunologic assays.

### 3. PARTICIPANT SELECTION

#### 3.1 Eligibility Criteria

- 3.1.1 Participant must have multiple myeloma and have relapsed following or are refractory to proteasome inhibitors, IMiDs and anti-CD38 mAb therapy
- 3.1.2 Participant must have at least 3 prior lines of therapy
- 3.1.3 Age  $\geq$ 18 years.
- 3.1.4 ECOG performance status  $\leq$ 2
- 3.1.5 Participant must have  $>$  20% plasma cells in the bone marrow core or aspirate differential  $<$ 30 days prior to enrollment.
- 3.1.6 ANC  $>$  1K/uL; Platelets  $>$  50 K/uL without transfusional support
- 3.1.7 Participant must have normal organ function as defined below:
  - total bilirubin  $\leq$ 1.5  $\times$  institutional upper limit of normal
  - AST(SGOT)  $\leq$ 3  $\times$  institutional upper limit of normal
  - ALT(SGPT)  $\leq$ 3  $\times$  institutional upper limit of normal
  - creatinine clearance  $\geq$ 40 mL/min for participants with creatinine levels above institutional normal.
- 3.1.8 The effects of DC/MM fusion and nivolumab on the developing human fetus are unknown. For this reason, women of child-bearing potential and men must agree to use adequate contraception (hormonal or barrier method of birth control; abstinence) prior to study entry and for the duration of study participation. Should a woman become pregnant or suspect she is pregnant while she or her partner is participating in this study, she should inform her treating physician immediately. Men treated or enrolled on this protocol must also agree to use adequate contraception prior to the study, for the duration of study participation, and 5 months after completion of treatment.
- 3.1.9 Ability to understand and the willingness to sign a written informed consent document.

